9.4.2 Secondary Endpoints

The analysis on secondary objectives will be based on the Per Protocol Set (PPS) for immunogenicity, as shown in [Table 12](#). If, in any study group and at any time point, the percentage of vaccinated participants with serological results excluded from the PPS for analysis of immunogenicity is 10% or more, a second-line analysis based on the Full Analysis Set (FAS) for immunogenicity will be performed to complement the PPS analysis.

Table 12 Secondary Endpoints-Statistical Analyses

Endpoint	Statistical Analysis Methods
Secondary immunogenicity	
For each study group with participants in Europe, for each sampling time point, and for each antigen*, the following statistics will be computed:
 
 • Unadjusted GMCs with 95% CI of anti-serotype specific IgG* before and 28 days after each study intervention administration as measured by in-house ELISA. • Unadjusted within-participant GMRs with 95% CI at 28 days after each study intervention administration compared to each study intervention administration baseline of anti-serotype specific IgG* as measured by in-house ELISA. • The number and percentage of participants with at least a 4-fold increase in Anti-serotype specific IgG* antibody concentration 28 days after each study intervention administration compared to first study intervention administration baseline, with 95% CI as measured by in-house ELISA. • The number and percentage of participants with Anti-S. Typhi Vi Ag IgG antibody concentrations equivalent to $\geq 4.3 \mu\text{g/mL}$, before and 28 days after each study intervention administration, with 95% CI as measured by in-house ELISA. • Unadjusted between-group ratio of GMC with 95% CI between iNTS-TCV groups and iNTS-GMMA and TCV groups will be computed for each anti-serotype specific IgG*, visit, and administration. 
For each study group with participants in Africa, for each sampling time point, and for each antigen*, the following statistics will be computed:
 
 • Unadjusted GMCs with 95% CI of anti-serotype specific IgG* before and 28 days after each study intervention administration as measured by in-house ELISA. • Unadjusted within-participant GMRs with 95% CI at 28 days after each study intervention administration compared to each study intervention administration baseline of anti-serotype specific IgG* as measured by in-house ELISA.

Endpoint	Statistical Analysis Methods
	
 The number and percentage of participants with at least a 4-fold increase in Anti-serotype specific IgG* antibody concentration 28 days after each study intervention administration compared to first study intervention administration baseline, with exact 95% CI as measured by in-house ELISA. The number and percentage of participants with Anti-S. Typhi Vi Ag IgG antibody concentrations equivalent to $\geq 4.3 \mu\text{g/mL}$, before and 28 days after each study intervention administration, with 95% CI as measured by in-house ELISA. Unadjusted between-group ratio of GMC with 95% CI between iNTS-TCV groups and iNTS-GMMA and TCV groups will be computed for each anti-serotype specific IgG*, visit, and administration. 
* Anti-S. Typhi Vi Ag total IgG, Anti-S. Typhimurium O Ag total IgG, Anti-S. Enteritidis O Ag total will be tested.
 
The GMCs, GMRs, and ratio of GMC along with 95% CIs will be obtained by exponentiating (base 10) the means and the lower and upper limits of the 95% CIs of the log-transformed values (base 10).
 
For the between-group assessments, the ANOVA model will be fitted based on the participants having a result at both the baseline and the considered time point. Immunogenicity data from full dose group in Europe will be pooled with those from full dose group in Africa if p-value associated to parameter for Center*Treatment interaction from ANOVA model ≥ 0.10 (ie, suggesting that impact of treatment on immunogenicity endpoint does not depend on center).
 
In that case, GMC, GMRs, and ratio of GMC will be calculated for entire full dose group (ie, Europe + Africa) adjusted by center. ANOVA model will include both vaccine group and center group as fixed effects, and adjusted GMC, GMRs, and ratio of GMC will be derived by exponential transformation of the corresponding group contrast in the model.
 
A sensitivity analysis will be performed pooling Europe and Africa data and adjusting treatment effect for center variable, regardless of the center*treatment associated p-value.
 
A second sensitivity analysis will be performed pooling Europe and Africa and adjusting treatment effect for race variable.
 
Finally, subgroup analysis will be performed by race.

Secondary Safety	
The number and percentage of participants reporting SAEs from 28 days after third study intervention administration (Day 197) up to Day 337 will be tabulated by study intervention group in Stage 1/Stage 2.
 
Number of participants with AEs/SAEs leading to withdrawal from the study, from 28 days after third study intervention administration (Day 197) up to Day 337, by study intervention group in Stage 1/Stage 2.

Abbreviations: Ag = Antigen; ANOVA = analysis of variance; CI = confidence intervals; ELISA = enzyme-linked immunosorbent assay; GMC = geometric mean concentrations; GMR = geometric mean ratios; iNTS-GMMA = invasive nontyphoidal *Salmonella*-generalized modules for membrane antigens; iNTS-TCV = invasive nontyphoidal *Salmonella*-typhoid conjugate vaccine; SAE = serious adverse event; S. Typhi = *Salmonella* Typhi; S. Typhimurium = *Salmonella* Typhimurium; TCV = typhoid conjugate vaccine

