4.2 Scientific Rationale for Study Design

The European Medicine Agency’s “Guideline on strategies to identify and mitigate risks for first-in-human (FIH) clinical trials with investigational medicinal products; (EMEA/CHMP/SWP/28367/07 Rev 1)”, is intended to assist Sponsors in the transition from nonclinical to early clinical development. It outlines factors influencing risk to be considered in the nonclinical testing strategy and designs of FIH clinical studies or investigational medicinal products. This guideline applies to all new chemical and biological investigational medicinal products except gene and cell therapy products. This guideline also applies to relevant Clinical Trial Authorization applications submitted in accordance with Directive 2001/20/EC (EU No 536/2014).

The study is designed in 2 stages to allow for the evaluation of the vaccine safety and immunogenicity across 2 geographic locations. This allows an assessment of the vaccine in both low and high endemicity settings and evaluate the potential impact of environmental exposure on the vaccine immune response. The first stage of the trial

which is the First Time in Human part of the trial is designed with the required safety measures to serve as risk mitigation (refer to Section 2.3.2). The vaccination schedule is selected based on the number of doses expected to be immunogenic in the target population for primary immunization with the vaccine if eventually licensed (ie, young infants from 6 weeks of age). The specific time points are selected to allow integration with existing Expanded Programme on Immunization schedules in the target regions for the vaccine (ie, 6 weeks, 14 weeks, and 9 months of age). Evaluating the safety of three doses in adults will allow the eventual testing of the same number of doses in the target population.

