The above tabulations may be performed by LLOQ status at baseline (above or equal to cut-off versus below the cut-off) for all 3 components, data permitting.

Only for S. Typhi Vi component the above tabulations may be performed by Anti-S. Typhi Vi Ag IgG antibody concentrations status at baseline as measured by ELISA ($>=$ [CC1] and $<=$ [CC1], $>=$ [CC1] and $<=$ [CC1]), data permitting.

Linear mixed model with repeated measures (MMRM) will be used to perform pairwise comparison between full doses of iNTS-TCV and iNTS-GMMA + TCV at Day 29, Day 57, Day 85, Day 169 and Day 197. The model will use fixed effects for center, treatment, time point, treatment*time point, center*treatment, baseline immunogenicity value as covariate, and a repeated time point effect within a participant under an unstructured covariance matrix. Variance between the groups will not be considered equal unless the assumption leads to convergence issues. Additional covariance structures and suitable transformation (e.g., log) may be explored to attain convergence and meet model assumptions, respectively. This analysis will be performed for full doses of iNTS-TCV and iNTS-GMMA + TCV from both the stages.

```
proc mixed data=indsn;  by parameter;  
  class subjid center trta avisit;  
  model aval=center trta avisit trta*avisit center*trta baseline/ddfm=satterth;  
  repeated avisit/subject=subjid type=un group=trta;  
  lsmeans trta*avisitn/pdiff cl alpha=0.05;  
  run;
```

In this analysis, immunogenicity data from full dose group in Europe will be pooled with those from full dose group in Africa if p-value associated to parameter for center*treatment interaction from MMRM model ≥ 0.10 (i.e., suggesting that impact of treatment on immunogenicity endpoint does not depend on center). In that case, GMC, GMRs, and ratio of GMC will be calculated for entire full dose group (i.e., Europe + Africa) adjusted by center from the above MMRM model without the center*treatment interaction term.

In case center*treatment interaction term is significant (i.e., p-value <0.1) the following analyses will be performed: 1) main analysis including center*treatment interaction term and GMC ratio separately for Europe and Africa will be produced from model with center*treatment interaction term, 2) sensitivity analysis excluding center*treatment interaction and GMC ratio for pooled Europe and Africa will be produced from model without center*treatment interaction term.

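### The center-by-treatment test can justify pooling Europe and Africa for the GMC ratio, but not for the model-adjusted GMC and GMR levels that the plan pools with it

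*Protocol*

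**What the plan says.** Protocol section 9.4.2, Table 12, sets the pooling threshold at a center-by-treatment p-value of 0.10 or more. The reason given is that such a result is "suggesting that impact of treatment on immunogenicity endpoint does not depend on center". The following sentence reads "In that case, GMC, GMRs, and ratio of GMC will be calculated for entire full dose group (ie, Europe + Africa) adjusted by center". SAP section 15 uses the same threshold in its repeated-measures model and again pools all three: "GMC, GMRs, and ratio of GMC will be calculated for entire full dose group (i.e., Europe + Africa) adjusted by center".

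The SAP's summary table then makes the model without the interaction the main analysis, with no sensitivity analysis. For the opposite result ("In case center*treatment interaction term is significant (i.e., p-value <0.1) the following analyses will be performed"), the SAP names only the GMC ratio as output, separately for Europe and Africa and then pooled. The protocol's pooling whatever the p-value is likewise worded for the treatment effect: "A sensitivity analysis will be performed pooling Europe and Africa data and adjusting treatment effect for center variable, regardless of the center*treatment associated p-value".

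Center weights are not stated in words in either document. The printed SAP code has "lsmeans trta*avisitn/pdiff cl alpha=0.05", with no weighting option.

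Three other places matter. Protocol section 3.0 sets separate immunogenicity objectives for European and African adults, and none for a combined population. Section 4.2 says of the two-stage design: "This allows an assessment of the vaccine in both low and high endemicity settings", and that it will "evaluate the potential impact of environmental exposure on the vaccine immune response". Table 12 and SAP section 15 also tabulate unadjusted GMCs and within-participant GMRs for each group in each stage, whatever the interaction test shows.

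**The concern.** The stated reason for pooling supports one common quantity, the ratio between iNTS-TCV and the separately administered vaccines. A GMC or a within-participant GMR is a mean within one arm on the log scale, so it moves with the center. Neither document asks for a look at the center main effect before levels are merged. This is a mismatch between the test and the quantity, so a larger trial would not cure it.

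At stake is how the adjusted results are read. When the p-value is 0.10 or more, the main model's adjusted levels are specified only in pooled form, although every immunogenicity objective concerns one population. A reader could take the pooled GMC or fold rise as a value for European or African adults when it may be neither.

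**Working it through.** **The plan's own figure first.** The documents give no power, effect size or SD. The one sample-size result is 133 evaluable out of 155 with 12% dropout per group (Protocol section 9.2). Rounding 0.88n down in each group of Protocol Table 4 (4, 4, 2, 16, 16, 8, 45, 45, 15) gives 3 + 3 + 1 + 14 + 14 + 7 + 39 + 39 + 13 = 133, so the figure reproduces. The full-dose arms therefore have about 14 evaluable each in Europe and 39 each in Africa.

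**What the test sees.** Let m be mean log10 concentration, with E and A for center and 1 and 2 for regimen. The interaction is

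(mE1 − mE2) − (mA1 − mA2).

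Add any constant c to both African means and it cancels. The test is blind to a center difference in level, however large.

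**What the pooled level becomes.** Let k be the Africa/Europe GMC ratio, the same in both arms. With center weights w and 1 − w for Africa and Europe, the pooled GMC is k^w times Europe's and k^(w−1) times Africa's. Equal weights (w = 1/2) are the default of the printed LSMEANS statement. Weighting by evaluable participants gives w = 39/53.

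| Assumed k | Equal weights: × Europe / × Africa | Participant weights: × Europe / × Africa |
|---|---|---|
| 1 | 1.00 / 1.00 | 1.00 / 1.00 |
| 2 | 1.41 / 0.71 | 1.67 / 0.83 |
| 3 | 1.73 / 0.58 | 2.24 / 0.75 |
| 5 | 2.24 / 0.45 | 3.27 / 0.65 |

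A GMR follows the same rule. If one center had a 40-fold rise and the other a 4-fold rise (invented values), equal weighting would report √(40 × 4) = 12.6-fold.

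**Whether the interval would give warning.** For an additive two-way ANOVA with equal center weights, the standard error of an arm's pooled log10 mean is

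SD × √[0.25 × (1/28 + 1/78) + 0.25 × 2/53] = 0.147 × SD.

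With an assumed SD of 0.5 this is 0.073. At k = 2 the pooled mean lies log10(2)/2 = 0.151 from each center's mean, or 2.05 standard errors. The 95% interval then covers a given center's true GMC with probability about Φ(1.98 − 2.05) = 0.47. At k = 3 the distance is 0.239, or 3.25 standard errors, and coverage is about 0.10. A simulation of 20,000 trials per case gave 0.47 and 0.10, and 0.95 at k = 1. For SD 0.4 to 0.6, the same formula gives 0.28 to 0.61 at k = 2 and 0.02 to 0.23 at k = 3.

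**Limits of the check.** k and the SD are assumptions; the documents give neither. The interval calculation uses the protocol's ANOVA. The SAP model adds a baseline covariate and repeated visits. The covariate could absorb part of a center difference, and by default the pooled level would then be evaluated at the overall mean baseline, which need not be that of either population.

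**The case against.** The strongest reply is that nothing rests on the pooled level. Protocol section 9.1 has no formal hypotheses, and section 9.6.2 calls the comparisons exploratory. The pooling text is introduced for between-group assessments, and the ratio, its main product, is sound on this point. The pooled means are labeled as adjusted for center, and by-stage values are always printed. An equal-weight average over centers is also a legitimate target if it is named. All of this stands, and it confines the point to the model-adjusted levels.

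Three stronger readings might be inferred, and the documents do not support them.

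- *The pooled levels necessarily misdescribe both populations.* That is true only if the levels differ; at k = 1 the pooled value fits both. Section 4.2 speaks of a potential impact of exposure and gives no level data.
- *Pooling hides the Europe/Africa contrast.* It does not, because the unadjusted GMCs and GMRs by stage are reported in every case.
- *Pooling in about 90% of trials, whatever k is, measures the harm.* With no true interaction, that rate is simply 1 minus the 0.10 test level. It shows that the rule ignores k and nothing more.

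The equal weighting is also an inference. The printed code is for the starting model, which still contains the interaction, and its LSMEANS statement uses a visit variable that appears in neither the CLASS nor the MODEL statement. It reads as a sketch, so final code could weight differently. Participant weights change the figures, as the table shows, but not the argument.

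**Conclusion.** The point holds for the model-adjusted GMC and GMR. A non-significant center-by-treatment term can support a common GMC ratio; it gives no support for a common level, and the plan uses it for both. The size depends on an unknown center difference. With equal weights, an assumed 2-fold difference puts the pooled GMC 1.41-fold from each center's value, and a 3-fold difference 1.73-fold; with no difference there is no error. The by-stage unadjusted results and the validity of the pooled ratio are outside this point. It should be corrected because the remedy is cheap and the adjusted levels otherwise appear only in a form that answers none of the stated objectives.

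**What to change.** In Protocol Table 12 and SAP section 15, apply the pooling rule to the ratio of GMCs only. Give any model-adjusted GMC and within-participant GMR by center, evaluated at that center's mean baseline. If a pooled level is kept as a supplement, label it a center-averaged value, state the center weights in words, and print it beside the by-stage values.

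The cost is a change of wording and output shells, with no new data and no effect on sample size. One pooled summary level per group is lost or moved to a supplement. One practical matter needs settling: the SAP model has no center-by-time term, so adjusted levels by center and visit would need that term or separate fits by stage.

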9.4.3 Tertiary Endpoints

The analysis on tertiary objective will be based on the PPS for immunogenicity, as described in [Table 13](#). If, in any study group and at any time point, the percentage of vaccinated participants with serological results excluded from the PPS for analysis of immunogenicity is 10% or more, a second-line analysis based on the FAS for immunogenicity will be performed to complement the PPS analysis.

Table 13 Tertiary Endpoints-Statistical Analyses

CCI

9.5 Missing Data

Data from participants who withdraw from the study, including AEs and any follow-up, will be included in the analyses of primary, secondary, and tertiary outcomes. Missing data will not be imputed.

9.6 Interim Analyses

A group-unblinded interim analysis for immunogenicity will be performed 28 days after the second administration in all study participants in Stage 2 in order to support the preparation for future studies.

9.6.1 Sequence of Analyses

All analyses before unblinding will be conducted on data as clean as possible.

The sequence of interim and final analyses will be the following:

- a. A group-unblinded interim analysis will be performed for all immunogenicity data accumulated up to 28 days after second intervention (Day 85) administration in Stage 2. At this point, the statistician will be unblinded for the analysis (ie, will have access to individual participant treatment assignments). The remaining study personnel will stay blinded (ie, will not have access to the individual participant treatment assignment) until Day 197. It is possible however, due to limited sample size, that unblinding occurs for a few participants having as specific AE or SAE (eg, an AE/SAE occurring only in a single group). Therefore, anyone having access to the analysis of Day 85 could become unblinded regarding those specific cases. The study will be considered as a single-blind from this point onwards. Results from immunogenicity analysis in Stage 2, and if applicable, in participants receiving the full dose in Stage 1/Step 2 will help with the design and approach in subsequent studies. No individual listings or data with the participants identifying information will be disseminated. The investigators and the participants will not have access to the treatment allocation up to study end (Day 337).
- b. After unblinding of the Sponsor personnel (partial observer-blind), an analysis on all data up to and including Day 197 (Visit 9) will be performed and individual listings will be generated. Data collected during the extended safety follow-up period will be analyzed after Day 337.
- c. A final CSR will be produced after the analysis after Visit 9 in Stage 2 and the analysis after Day 337 will be included in an integrated CSR to be written after.

9.6.2 Statistical Considerations

Comparative analyses will be exploratory and should be interpreted with caution considering that there is no adjustment for multiplicity and that the study is not powered for such comparisons.

9.7 Internal Safety Review Committee

An iSRC will be established to monitor the safety of participants throughout the trial and, more specifically, to recommend whether proceeding from low dose in Stage 1/Step 1 to the full dose in Stage 1/Step 2 is permissible, based on the accumulated safety data. They will also recommend proceeding the clinical testing of the vaccine in African participants in Stage 2 based on the post-primary safety results in Stage 1 (iSRC #3). The iSRC will include study-independent GSK members and an external, non-GSK clinical development expert to ensure an unbiased assessment.

Planned safety data reviews are specified in [Figure 1](#) and in [Table 14](#). After the reviews, if no safety signal is observed, the favorable outcome of the safety evaluations will be documented and provided in a written way, authorizing the Investigator to start the administration of the subsequent dose of study intervention to participants, as well as enrollment and study intervention administration to the remaining participants in the next step of the study, as described in the protocol. If a safety signal is observed during the safety evaluations or if any of the holding rules are met, the iSRC Chair (or his/her representative) is responsible for the urgent communication to GVGH PP, including the rationale for the decision to put the study intervention administration on hold or not.

The IQVIA study project lead will be accountable for notifying all investigators of the decision whether to suspend, modify or continue the conduct of the study on all groups or on selected groups.

In Stage 1/Step 1, there will be a sequential approach in which the 10 sentinel participants will receive the first low dose of the study interventions on consecutive days. The sentinel participants will receive a safety phone call for safety surveillance on the day following first study intervention administration (Day 2), before proceeding with administration of study intervention in subsequent participants. If the Investigator becomes aware of a holding rule being met, he/she must suspend administration of the study intervention and inform the Sponsor's delegate immediately.

In Step 2, a second sentinel of 10 participants vaccinated on consecutive days. They will receive a phone call for safety surveillance on the day following the first study intervention administration (Day 2), before proceeding with study intervention administration in the subsequent participants. The remaining 30 participants will be vaccinated at least 60 minutes apart.

Likewise, in Stage 2, the first 21 participants will receive the study interventions sequentially, at least 60 minutes apart, with a safety phone call/home Visit the day after administration for safety surveillance.

All 155 participants in the study (Stage 1 and Stage 2) will be closely monitored at the site for at least 60 minutes post-administration for safety surveillance.

Seven days after the first study intervention administration in the low dose cohort (Step 1) in Stage 1 is completed, an iSRC will receive a summary of all available safety data (solicited administration site events and systemic events, unsolicited AEs and SAEs) and listings of hematology and blood chemistry test values obtained following the first study intervention administration (baseline and 7 days after study intervention administration). Based on evaluation of the safety data (review #1, [Table 14](#)), the iSRC will make a recommendation, as to whether the next stage of the trial (Stage 1/Step 2), when the administration of the full dose of the study interventions to the study participants, should start.

Seven days after all participants in Stage 1/Step 1 have received their second study intervention, there will be an iSRC review of all safety data collected up to day 7 after second administration (Day 64) in Step 1 (review #2, [Table 14](#)). If there is no safety concern with any of the investigational groups, the second study intervention administration in Stage 1/Step 2 can commence.

There will be another iSRC data review 28 days after the second administration in Stage 1/Step 2 (review #3, [Table 14](#)). In the case of a favorable review, recruitment of participants in Stage 2 in Africa can commence.

All the participants in Stage 1 will complete the trial according to the schedule. A final safety evaluation of all data collected in Stage 1 will be performed once the study is completed.

The first 21 participants in Stage 2 will receive the study interventions sequentially, 60 minutes apart, with a follow-up safety phone call/home Visit conducted one day after the first administration to identify any safety concerns in the participants who received the study interventions. The Investigator will proceed with study interventions administration in the subsequent study participant only in the case that there is no safety concern in the previous participant who received the study interventions. If the Investigator becomes aware of a holding rule being met, he/she must suspend administration of the study intervention and inform the Sponsor's delegate immediately.

Seven days after the first administration of the study interventions of the first 21 participants in Stage 2, there will be an iSRC to review all available safety data collected (review #4, [Table 14](#)). Following this, in the event of a positive safety review, the 84 remaining participants will receive the study interventions in parallel.

A last iSRC review analysis for safety will be performed 28 days after second administration in the first 21 participants in Stage 2 to allow the third study intervention administration of all participants in Stage 2 and to support preparation for future studies (review #5, [Table 14](#)).

A summary of the planned unblinded iSRC reviews for the trial are presented in [Table 14](#). In case of any safety concerns, ad hoc iSRC reviews may be called.

Instream blinded monitoring will also be performed by the internal GSK Safety Review Team (SRT); details of these blinded data reviews for the trial are presented in [Table 15](#).

Table 14 Summary of the iSRC Reviews*

iSRC #	Timing of Safety Evaluation	Subsequent Activities
1	7 days after first administration with low dose of 10 sentinel participants in Step 1 (Stage 1)	First administration with full dose of 40 participants in Step 2 (Stage 1)
2	7 days after second administration with low dose of 10 sentinel participants in Step 1 (Stage 1)	Second administration with full dose of 40 participants in Step 2 (Stage 1)
3	28 days after second administration with full dose of 40 participants in Step 2 (Stage 1)	First administration with full dose of first 21 participants in Stage 2
4	7 days after first administration of first 21 participants in Stage 2	First administration of remaining 84 participants in Stage 2
5	28 days after second administration in the first 21 participants in Stage 2	Third administration with full dose of all participants in Stage 2

Abbreviation: iSRC= Internal Safety Review Committee

* All available safety data will be cumulatively reviewed at each safety evaluation.

Table 15 Time points for Blinded Instream Monitoring

Stage #	Instream Monitoring
Stage 1 (Steps 1 and 2)	All cumulative data (all subjects) up to 7 days post-first vaccination
	All cumulative data (all subjects) up to 7 days post-second vaccination
	All cumulative data (all subjects) up to 7 days post-third vaccination
Stage 2	All cumulative data (all subjects) up to 7 days post-first vaccination of the additional 84 subjects
	All cumulative data (all subjects) up to 28 days post-first vaccination of the additional 84 subjects
	All cumulative data (all subjects) up to 7 days post-second vaccination of the first 21 subjects
	All cumulative data (all subjects) up to 28 days post-second vaccination of the additional 84 subjects

